### 3.1.4 SC Phase

One week (7 days) after the second IV dose (IV#2), subjects will return to the clinic to begin the weekly SC administrations of IGSC 20%. The SC Phase will continue for a total of 24 weeks (6 months). The initial weekly SC dose is calculated as described in [Section 3.3.2](#). Briefly, the SC dose is calculated using the following formula:

$$\frac{300 \text{ to } 800 \text{ mg/kg (IV dose)}}{3 \text{ or } 4 \text{ (regular IV dosing interval in week)}} \times 1.37 \text{ (IV to SC dose adjustment factor)}$$

After 12 weeks (3 months) of weekly SC therapy, determination of PK profiles for total IgG during the SC Phase will begin at the blood draw just prior to the 13th SC infusion with the last sample collected immediately prior to the 14th SC infusion (7 days total).

The detailed study flow chart and specific time points for PK sampling for IV IGIV-C 10% and SC IGSC 20% administration are outlined in [Figure 3-2](#).

**Figure 3-2 IV dosing of IGIV-C 10% and SC dosing of IGSC 20% Clinic Visits and PK sampling schedules (Also see Sections 3.6.2.3 and 3.6.2.4)**

### 3.1.5 Interim PK Analysis

The dosing regimen for SC administration of IGSC 20% is based on literature data of the bioavailability of subcutaneous administered IgG and prior experience with SC IGIV-C 10%. The weekly IGSC 20% dosing regimen to be evaluated herein (1.37 times the currently stable IV IgG dose divided by 4 for subjects on an every-4-week dosing schedule or divided by 3 for subjects on an every-3-week dosing schedule) is predicted to provide an steady-state AUC of total IgG levels not inferior to that of the prior IV dose based on the established bioequivalence acceptance data.

While it is believed that a dose adjustment factor of 1.37 for determining an SC dose of IGSC 20% (from an IV dose) is suitable, an interim PK analysis is planned to confirm that this SC dose adjustment factor calculation is adequate and to allow for potential modification of the dose adjustment factor if necessary. The interim PK analysis will be performed as soon as practical after the first 6 adult/adolescent subjects (age  $\geq 12$ -75 years) have completed the steady-state PK sampling schedule for both the IV (IV#2) and SC Phases (SC#14) of the trial. Data from these 6 adult/adolescent subjects will be analyzed using standard PK and statistical methodology (Section 5) to evaluate and compare the  $AUC_{0-\tau}$ 's of total IgG from the IV administration of IGIV-C 10% and SC administration of IGSC 20%.

The outcome of this interim analysis will determine whether the dose adjustment factor will be modified. If the ratio of geometric LSM for  $AUC_{0-7, SC}$  vs. adjusted  $AUC_{0-7, IV}$  falls below 10% of the desired 1.0 (ie,  $<0.9$ ), and the mean trough concentrations for the SC administration of IGSC 20% falls below the target level in more than 3 of the 6 adult/adolescent subjects, then a dose adjustment factor increase would be implemented to ensure that the subjects receive an optimal IGSC 20% and are not susceptible to potential bacterial infections.

If the ratio of geometric LSM for  $AUC_{0-7, SC}$  vs. adjusted  $AUC_{0-7, IV}$ , achieves  $\geq 0.9$ , there will be no change in the dose adjustment factor.

Subjects enrolled early in the trial may complete their regularly scheduled 24 weeks of SC therapy on the initial IGSC 20% dose before a decision from the interim analysis is available. In this event, these subjects will continue to receive weekly SC infusions of IGSC 20% until the interim PK analysis deems whether or not a new dose adjustment factor would be required. Subjects will return to the study center every 4 weeks for evaluation and have the same study procedures performed as those at SC Week#21 with (at less frequent intervals) safety laboratory assessments, IgG subclass levels, and specific antibody titers for *S. pneumoniae*, *H. influenzae*, and *C. tetani* (tetanus) every 8 weeks as detailed in Section 3.6.2.5. This will continue until the interim analysis is completed. If the results of the interim analysis do not indicate a need for a dose adjustment factor change, subjects will be brought into the clinic and end of study procedures will be performed.

If the need for changing the dose adjustment factor arises, the revised dose adjustment factor will be calculated based on the ratio of the geometric LSM for  $AUC_{0-7, SC}$  vs. adjusted  $AUC_{0-7, IV}$  with consideration of mean trough levels obtained from the SC administration of IGSC 20%.

The revised dose adjustment factor will be communicated to sites and the revised dose adjustment factor would be applied to the subjects' next SC infusion of IGSC 20% in the clinic, which should be scheduled as soon as possible, upon receiving formal notification from the Sponsor. These subjects will re-commence at SC#1 with the new dose adjustment factor. All subjects will be required to have a minimum of 24 weekly SC infusions of IGSC 20% with the new dose adjustment factor. For subjects currently in the SC Phase or who have completed the 24 weeks of the SC Phase and are continuing on treatment until the results of the interim PK analysis are available, subjects will be required to continue in the SC Phase with the revised dose adjustment factor for 24 weekly SC infusions. In both of the above situations, all subjects will have a repeat complete IGSC 20% PK profile after 12 weeks on the new dose adjustment factor (same assessment as initial SC Week #13). The time points for PK blood sample collection will be those outlined in [Figure 3-2](#) and [Section 3.6.2.4](#).

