Subjects, depending on their current IgG treatment regimen, may be required to enter the Run-In Phase to receive IV IGIV-C 10% treatment (Sponsor provided) to achieve an approximately steady-state condition prior to entering the IV Phase. They will then enter the IV Phase to determine the AUC profiles of IV infusions of IGIV-C 10%.

Subjects with a qualifying IV IGIV-C 10% treatment regimen (on stable IGIV-C 10% doses of 300-800 mg/kg) can enter the IV Phase directly where they will receive IGIV-C 10% (Sponsor provided). In the IV Phase, steady-state IV PK assessments including AUC will be performed.

After completing the IV Phase, subjects will enter the SC Phase to receive weekly SC doses of IGSC 20% for at least 24 weeks. The IGSC 20% dose will be determined by using an initial IV to SC dose adjustment factor of 1.37. After reaching an approximately steady-state condition, the SC PK profiles including AUC at SC Week #13 will be determined.

Comparison of the IV PK profiles and IGSC 20% PK profiles in the first 6 adult/adolescent subjects will be performed through an interim PK analysis. If the dose adjustment factor is deemed acceptable (SC dose of IGSC 20% is non-inferior to the subject's IV dose) ([Section 3.1.5](#)), all subjects will continue to complete treatment and assessments through Week#25 (no further monthly extension visits). Otherwise, a new dose adjustment factor will be employed for all subjects following the procedures described in [Section 3.1.5](#), and subjects will receive 24 weeks of IGSC 20% treatment at the new IGSC 20% dose. In this study, the PK profiles will be assessed in all subjects. Subjects aged 2 to 5 years old will be assessed using an abbreviated sampling schedule for PK profiles.

The interim serial PK samples (for both the IGIV-C 10% IV and the IGSC 20% SC dosing phases) may be obtained at an alternate location. If an outside agency is utilized for sample collection, the samples will be drawn and processed per protocol and laboratory manual instructions.

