Grifols Study 060001 showed that weekly SC administration of IGIV-C 10% in 32 adult/adolescents PI subjects resulted in a relatively constant steady-state trough concentration of total IgG (1140 mg/dL). The steady-state trough levels of IgG following SC infusions were found to be 19% higher than those from IV infusions. There were no SBIs reported in the 24-week SC treatment phase (34). This study demonstrated that the 1:1.37 IV to SC dose adjustment factor produced a point estimate for the geometric least squares mean (LSM) ratio of  $AUC_{SC}$  vs.  $AUC_{IV}$  of 0.888, with a 90% confidence interval (CI) of 0.861 to 0.917 (analysis of variance [ANOVA]). The lower bound of the 90% CI was above 0.80 indicating that the SC dose was non-inferior to the IV dose in terms of AUC. In addition, the 90% CI was within the limit of 0.80 to 1.25, a criterion for concluding “bioequivalence” between the 2 treatments (SC and IV doses of IGIV-C 10%).

Additionally, a recently completed pediatric study (Grifols Study T5004-401) of weekly SC administration of IGIV-C 10% in 11 pediatric subjects (age range 4-15 years) also resulted in no SBI reported in the 12-week SC treatment period. The mean steady-state minimum concentration ( $C_{trough}$ ) of total IgG was 1325 mg/dL following weekly SC infusion of IGIV-C 10% which was 31% higher than that of the IV dosing  $C_{trough}$  (997 mg/dL) (1.37 dose adjustment factor relative to IV). The mean of the ratios of SC AUC vs. IV AUC was also favorable (mean  $\pm$  SD: 1.05  $\pm$  0.104).

Accordingly in this study, a 1:1.37 IV to SC dose adjustment factor will be initially employed for the transition from IVIG to IGSC 20% treatment and will be evaluated in the interim PK analysis ([Section 3.1.5](#)).

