The interim serial PK samples (for both the IGIV-C 10% IV and the IGSC 20% SC dosing phases) may be obtained at an alternate location. If an outside agency is utilized for sample collection, the samples will be drawn and processed per protocol and laboratory manual instructions.

Comparison of the IV PK profiles and IGSC 20% PK profiles in the first 6 adult/adolescent subjects will be performed through an interim PK analysis. If the dose adjustment factor is deemed acceptable (SC dose of IGSC 20% is non-inferior to the subject’s IV dose) (Section 3.1.5), all subjects will continue to complete treatment and assessments through Week#25 (no further monthly extension visits). Otherwise, a new dose adjustment factor will be employed for all subjects following the procedures described in Section 3.1.5, and subjects will receive 24 weeks of IGSC 20% treatment at the new IGSC 20% dose. In this study, the PK profiles will be assessed in all subjects. Subjects aged 2 to 5 years old will be assessed using an abbreviated sampling schedule for PK profiles.

The overall study design is depicted in Figure 3-1 and Figure 3-2. The subject entry criteria are described in Table 3-1.

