The hypothesis to be tested is that the weekly SC dose of IGSC 20% will achieve an approximate steady-state  $AUC_{0-\tau,SC}$  of total IgG that is non-inferior to that achieved by a regular IV dose of IGIV-C 10% ( $AUC_{0-\tau,IV}$  divided by 3 or 4 depending on the IV dosing intervals). Non-inferiority of steady-state IgG AUC between SC dose of IGSC 20% and IV IGIV-C 10% administration will be tested based on established regulatory guidelines for bioequivalence testing. The 90% CI of the geometric LSM ratio of SC AUC to IV AUC will be calculated. The SC dose is considered to be non-inferior to the IV dose if the low bound of the 90% CI for the geometric LSM AUC ratio is above 0.80 based on loge-transformed data.

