#### 5.1.4 Interim PK Analysis

An interim PK analysis will be conducted as described in [Section 3.1.5](#). This analysis will be performed as soon as practical after the first 6 adult/adolescent subjects (aged  $\geq 12-75$  years) have completed the PK sampling schedule for both the IV and SC (after the 13th SC dose) Phases of the trial. PK data from these 6 adult/adolescent subjects will be analyzed using procedures as described in [Section 5.1.3](#) above. A decision on whether to modify the dose adjustment factor for calculating the SC dose will be made based on this interim PK analysis.

Final PK and statistical analysis will be based on the PK data obtained after the final (or adjusted, if any) SC dose administered in all completed subjects.

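### The protocol gives two different criteria for changing the SC dose adjustment factor at the interim, and Section 3.1.5 leaves one result without an outcome and its trough target without a value

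*Protocol*

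**What the plan says.** Section 3.1.5 bases the decision on the first six adult/adolescent subjects. The factor is increased if the point estimate of the geometric LSM ratio of SC AUC to adjusted IV AUC is under 0.9 and a second condition is met: "mean trough concentrations for the SC administration of IGSC 20% falls below the target level in more than 3 of the 6 adult/adolescent subjects". If the ratio is 0.9 or more, "there will be no change in the dose adjustment factor". The rule mentions neither a confidence interval nor 0.80.

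Section 3.1 describes the same decision differently. "If the dose adjustment factor is deemed acceptable (SC dose of IGSC 20% is non-inferior to the" IV dose, everyone completes treatment through Week 25. "Otherwise, a new dose adjustment factor will be employed for all subjects". The Synopsis (Overall Study Description) says the same: "Otherwise, a new dose adjustment factor will be employed for all subjects following the procedures described in" Section 3.1.5. Neither place has a trough condition.

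Section 5.1.3 gives the only definition of non-inferiority, repeated in the Synopsis: it holds "if the low bound of the 90% CI for the geometric LSM AUC ratio is above 0.80 based on loge-transformed data". Section 5.1.4 carries this analysis to the interim: "PK data from these 6 adult/adolescent subjects will be analyzed using procedures as described in" Section 5.1.3.

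Section 1.3.1 reports an earlier sponsor study of SC IGIV-C 10% at the same factor, 1.37, in 32 adults and adolescents. It found an AUC ratio "of 0.888, with a 90% confidence interval (CI) of 0.861 to 0.917", with SC troughs 19% above IV troughs.

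**The concern.** This is the trial's only adaptive decision, and it sets the SC dose for every subject. Under Section 3.1.5, a change restarts subjects at SC#1 with at least 24 further weekly infusions and a repeat PK profile. No change sends subjects who are waiting for the result to their end-of-study procedures. The study is open-label, so a rule that is not fixed in advance leaves the decision to judgement after the data are seen.

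There are three faults:

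- A point-estimate rule joined to a trough count is not the same rule as a confidence bound above 0.80.
- Section 3.1.5 covers three of its four ratio-by-trough combinations and is silent on the fourth.
- The trough target that triggers an increase has no value anywhere in the protocol.

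The silent combination is a realistic one. The earlier study's result (ratio below 0.9, SC troughs above IV) falls in it if the target is the IV trough.

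**Working it through.** **1. The two rules side by side**

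| Interim result | Section 3.1.5 | Synopsis / Section 3.1 |
|---|---|---|
| Ratio ≥0.9, lower bound >0.80 | no change | keep |
| Ratio ≥0.9, lower bound ≤0.80 | no change | change |
| Ratio <0.9, more than 3 low troughs, bound >0.80 | increase | keep |
| Ratio <0.9, more than 3 low troughs, bound ≤0.80 | increase | change |
| Ratio <0.9, 3 or fewer low troughs, bound >0.80 | not stated | keep |
| Ratio <0.9, 3 or fewer low troughs, bound ≤0.80 | not stated | change |

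Two rows are opposite decisions and two have no outcome in Section 3.1.5.

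**2. A plausible SD.** The protocol gives no SD for the within-subject log AUC ratio. From the earlier study's interval, taking all 32 subjects as paired:

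SD = [ln(0.917) − ln(0.861)]/2 ÷ t(0.95, 31) × √32 = 0.105.

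As a check on the input, √(0.861 × 0.917) = 0.889, which agrees with 0.888. An SD of 0.15 is used as a sensitivity assumption.

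**3. What non-inferiority requires with six subjects.** The smallest observed ratio that passes is 0.80 × exp(t(0.95, 5) × SD/√6), with t = 2.015:

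- SD 0.105: 0.872
- SD 0.15: 0.905

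The two thresholds coincide at 0.9 only when SD = ln(0.9/0.8) × √6/2.015 = 0.143. The rules can therefore conflict both ways. An observed 0.88 with four low troughs (SD 0.105) is keep under Section 3.1 and increase under 3.1.5. An observed 0.90 with a sample SD above 0.143 is change under Section 3.1 and no change under 3.1.5.

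**4. How often this would arise.** Simulation with n = 6 and 200,000 runs per setting. Assumptions: true ratio 0.888; target equal to the subject's own IV trough; trough ratio proportional to AUC ratio (1.19/0.888); log-trough SD 0.105 to 0.15. A trough/AUC correlation of 0 or 0.7 made no material difference.

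| Share of all interims | SD 0.105 | SD 0.15 |
|---|---|---|
| Ratio ≥0.9 | 38% | 41% |
| Unassigned cell in 3.1.5 | 62% | 58-59% |
| Unassigned, and Section 3.1 keeps | 31% | 10% |
| Unassigned, and Section 3.1 changes | 32% | 49% |
| Increase directed by 3.1.5 | <1% | <1% |
| Ratio ≥0.9 but non-inferiority not shown | 1% | 8% |
| Non-inferiority not shown, all cases | 33% | 57% |

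Components may differ from totals by rounding.

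**5. Dependence on the unstated target.** At a true ratio of 0.80, non-inferiority is not shown in 95% of interims. Section 3.1.5 directs an increase in 4-9% with the adult trough relation, or about 35% with the pediatric relation in Section 1.3.1 (1.31/1.05). At 0.70 the figures are 68-80% and 92-98%. No single action rate can be derived until the target is given.

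**6. Final test, 42 completers, factor unchanged.** It passes in 98% at a true ratio of 0.85 and about 100% at 0.888 (83% and 99.7% at SD 0.15).

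**The case against.** The best defence is that Section 3.1.5 is the single operative rule. The Synopsis and Section 3.1 are summaries that cite it, Sections 3.3.2.1 and 3.3.2.2 send any modification to it, and Section 5.1.4 opens by saying that the interim is conducted as described there. On this view, applying the Section 5.1.3 procedures could mean only deriving the AUCs and their ratio. The missing cell then has a natural default: an increase needs both conditions, so without both the factor stays.

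The figures can also be questioned. The only protective level the protocol mentions is 500 mg/dL, given as a literature level in Section 1.2 and used as a screening threshold, and it could be the intended target. The 62% rests on one true ratio from a different product; at SD 0.105 a ratio below 0.9 occurs in 40% of interims at a true 0.91 and 10% at 0.95. The example of 0.88 with four low troughs is very unlikely under the model used here (about 0.02% if troughs are independent), and outright opposite decisions are rare.

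The limits on the figures stand. The textual defence does not remove the conflict. The Synopsis and Section 3.1 state a criterion that Section 3.1.5 does not contain. The default is not written, since 3.1.5 states no change only for a ratio of 0.9 or more. If silence is read as no change, 3.1.5 contradicts the change clause in Section 3.1 whenever non-inferiority is not shown: 33% of interims at a true 0.888, or 57% at SD 0.15. A 500 mg/dL target would make low troughs rarer (the earlier study's SC trough was 1140 mg/dL) and so the empty cell more likely. An SAP might hold the target, but it cannot cure conflicting protocol passages, and 3.1.5 points to no other source for a value that triggers a dose change.

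**Conclusion.** The point holds in all three parts, and it should be corrected before the interim decision is taken. The contradiction, the missing outcome and the missing target are facts of the text and need no modelling. Their practical weight does depend on assumptions: with a true ratio of 0.888, the IV trough as target and an SD of 0.105 to 0.15, roughly six interims in ten would give a result for which Section 3.1.5 directs nothing, while Section 3.1 directs keep or change according to the interval. Directly opposite instructions are less common, at 1% to 8%. The harm is an undetermined dosing decision for all subjects, not a likely failure of the primary test.

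**What to change.** Reconcile the Synopsis (both the Overall Study Description and the Interim PK Analysis paragraph), Section 3.1, Section 3.1.5 and Section 5.1.4 into one interim decision rule. State it once, in Section 3.1.5, and only cross-reference it elsewhere. Give every combination of AUC and trough result an outcome, including a ratio below 0.9 with three or fewer low troughs. State the trough target as a number or as an explicitly defined quantity. Then simulate how often the chosen rule acts over a range of true ratios, for example 0.70 to 1.0, and compare this with the final 0.80 criterion. Which rule and which level to adopt is the sponsor's decision. The cost is amendment wording in these places and a short simulation, with no extra patients or samples.

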## 3.2 Selection of Study Population

Eligible participants for this study include male or female subjects who are 2 to 75 years of age and have a diagnosis of PI requiring IgG replacement treatment. Subjects who initially fail to meet eligibility criteria may be re-screened once upon consultation with the Sponsor. Subjects who fail to meet eligibility criteria upon re-screen are Screen Failures and will not be eligible to participate in the study.

### 3.2.1 Inclusion Criteria

A subject must meet all the following inclusion criteria to be eligible for participation in this study:

1. Subjects between the ages of 2 and 75 years (inclusive) at Screening.
2. Documented and confirmed pre-existing diagnosis of PI with features of hypogammaglobulinemia requiring IgG replacement therapy including but not limited to the following humoral-based immunodeficiency syndromes (eg, X-linked agammaglobulinemia, common variable immunodeficiency), and combined immunodeficiency syndromes without lymphocytopenia (eg, hyper immunoglobulin M [IgM] immunodeficiency syndrome). Please also refer to Exclusion Criteria.
3. The subject has not had a SBI within the last 3 months prior to or during Screening.
4. Currently on IgG replacement therapy (via IV or SC infusion) for  $\geq 3$  months.
5. *Note: This inclusion criterion is removed in protocol amendment 2.*
6. Screening trough IgG levels must be  $\geq 500$  mg/dL.

Note: If Screening trough levels are not above this threshold, the subjects will be a Screen Failure, but may be re-screened following dose adjustment of their original IgG replacement therapy regimen and maintaining stable dosing for a period of at least 3 months prior to Screening a second time.

7. The medical records for all subjects should be available to document diagnosis, previous infections, and treatment.
8. The subject has signed an informed consent.

Note: The subject must sign the informed consent form (ICF) if at least 18 years old; for children of younger age, the subject's parent or legal guardian must sign the ICF and if appropriate/applicable, the subject must sign a Child Assent form approved by the Institutional Review Board or Ethics Committee (IRB/EC) per their requirements (See [Section 7.4](#)).

### 3.2.2 Exclusion Criteria

A subject meeting any of the following exclusion criteria is NOT eligible for participation in the study.

1. Clinical evidence of any significant acute or chronic disease that, in the opinion of the Investigator, may interfere with successful completion of the trial or place the subject at undue medical risk
2. The subject has had a known serious adverse reaction to immunoglobulin or any severe anaphylactic reaction to blood or any blood-derived product
3. The subject has a history of blistering skin disease, clinically significant thrombocytopenia, bleeding disorder, diffuse rash, recurrent skin infections or other disorders where SC therapy would be contraindicated during the study
4. The subject has isolated IgG subclass deficiency, isolated specific antibody deficiency disorder, or transient hypogammaglobulinemia of infancy
5. The subject has known selective immunoglobulin A (IgA) deficiency (with or without antibodies to IgA)
6. Females of childbearing potential who are pregnant, have a positive pregnancy test at Screening (serum) or IV#1 Baseline (urine) (human chorionic gonadotropin [HCG]-based assay), are breastfeeding, or unwilling to practice a highly effective method of contraception (oral, injectable or implanted hormonal methods of contraception, placement of an intrauterine device [IUD] or intrauterine system [IUS], condom or occlusive cap with spermicidal foam/gel/film/cream/suppository, male sterilization, or true abstinence) throughout the study

Note: True abstinence: When this is in line with the preferred and usual lifestyle of the subject. (Periodic abstinence [eg, calendar, ovulation, symptothermal, post-ovulation methods], declaration of abstinence for the duration of a trial, and withdrawal are not acceptable methods of contraception.)

7. The subject has significant proteinuria (dipstick proteinuria  $\geq 3+$  or known urinary protein loss  $> 1$  g/24 h or nephrotic syndrome) and/or has a history of acute renal failure and/or severe renal impairment (blood urea nitrogen [BUN] or creatinine more than 2.5 times the upper limit of normal [ULN]) and/or on dialysis
8. The subject has Screening Visit values of aspartate aminotransferase (AST) or alanine aminotransferase (ALT) levels exceeding more than 2.5 times the ULN for the expected normal range for the testing laboratory.
9. The subject has hemoglobin  $< 9$  g/dL at Screening.
10. The subject has a history of or current diagnosis of deep venous thrombosis (DVT) or thromboembolism (eg, deep vein thrombosis, myocardial infarction, cerebrovascular

accident or transient ischemic attack); history refers to an incident in the year prior to Screening or 2 episodes over lifetime.

11. The subject is currently receiving anti-coagulation therapy which would make SC administration inadvisable (vitamin K antagonists, nonvitamin K antagonist oral anticoagulants [eg, dabigatran etexilate targeting Factor IIa, rivaroxaban, edoxaban, and apixaban targeting Factor Xa], parenteral anticoagulants [eg, fondaparinux]).
12. The subject currently has a known hyperviscosity syndrome.
13. The subject has an acquired medical condition that is known to cause secondary immune deficiency, such as chronic lymphocytic leukemia, lymphoma, multiple myeloma, chronic or recurrent neutropenia (absolute neutrophil count less than 1000/ $\mu$ L [ $1.0 \times 10^9$ /L]), or human immunodeficiency virus (HIV) infection/acquired immune deficiency syndrome (AIDS).
14. The subject has a known previous infection with or clinical signs and symptoms consistent with current hepatitis B virus (HBV) or hepatitis C virus (HCV) infection.
15. The subject (if < 18 years of age) has non-controlled arterial hypertension at a level of greater than or equal to the 90th percentile blood pressure (either systolic or diastolic) for their age and height (See [Appendix 3](#)) or the adult subject has non-controlled arterial hypertension (systolic blood pressure >160 mmHg and/or diastolic blood pressure >100 mmHg)
16. The subject is receiving any of the following medications: (a) immunosuppressants including chemotherapeutic agents; (b) immunomodulators; (c) long-term systemic corticosteroids defined as daily dose >1 mg of prednisone equivalent/kg/day for >30 days.  
Note: Intermittent courses of corticosteroids of not more than 10 days would not exclude a subject. Inhaled or topical corticosteroids are allowed.
17. The subject has known substance or prescription drug abuse
18. The subject has participated in another clinical trial within 30 days prior to Screening (observational studies without investigative treatments [non-interventional] are permitted) or has received any investigational blood product with the exception of other IgG products within the previous 3 months
19. The subject/caregiver is unwilling to comply with any aspect of the protocol, including the home SC infusions, blood sampling, and completion of a SC infusion diary for the duration of the study
20. Mentally challenged subjects who cannot give independent informed consent or assent
21. In the opinion of the Investigator, the subject may have compliance problems with the protocol and the procedures of the protocol

